6.2. Inclusion and Exclusion Criteria

All recorded inclusion/exclusion criteria status and deviations for subjects who passed Screening will be presented in a data listing.

6.3. Protocol Deviations

A major protocol deviation is a subset of protocol deviations defined as follows:

- Protocol deviations that may affect the interpretation of study results or the subject's rights, safety, or welfare.
- Protocol deviations thought to interfere with the absorption, distribution, metabolism, and excretion of the compound to be measured.

Major protocol deviations will be summarized by treatment arm and overall for the ITT population. Major protocol deviations leading to exclusion from PK population will be counted in the same table. All major protocol deviations will be presented in a data listing for the ITT population.

There were no major protocol deviations identified during the DRM.

7. Demographics and Baseline Characteristics

7.1. Demographics

Demographics and baseline characteristics will be summarized for the ITT and Safety populations by treatment arm and overall. The demographic characteristics will consist of age (years), gender (male, and female), ethnicity (Hispanic or Latino, Not Hispanic or Latino, Not Reported, and Unknown), and race (American Indian or Alaska Native, Asian, Black or African American, White, Other, and Multi-racial). Subjects who are from multiple races will be only counted in “Multi-racial” category and will not be counted in each specific race category. The baseline characteristics consist of whether New York Heart Association (NYHA) Functional Classification assessment was performed (yes or no), whether subject had any cardiac disease which can be classified by NYHA Functional Classification (yes or no), NYHA class (NYHA Class I, NYHA Class II, NYHA Class III, and NYHA Class IV), height (cm), weight (kg), and body mass index (BMI) (kg/m^2) which are measured at Screening, and weight category (body weight <80 kg and body weight ≥ 80 kg) which is measured on Day -1. For female subjects, female fertility status (surgically sterilized, post-menopausal, potentially able to bear children) will be presented.

Subject demographic and baseline characteristics will be presented in a data listing for the ITT population. The NYHA Functional Classification performed at Screening will be provided in a separate listing for the ITT population.

7.2. General Medical History

General medical history information is collected at the Screening visit and will be coded using Medical Dictionary for Regulatory Activities (MedDRA), Version 22.0 or higher. General medical history will be summarized by treatment arm and overall, system organ class (SOC), and preferred term (PT) using the number and percentage of subjects with at least one medical history for the ITT and Safety populations. The total number of medical history and the number and percentage of subjects with at least one medical history will also be presented in the table. At each level of subject summarization, a subject is counted once if the subject reported one or more findings. A listing of general medical history will also be provided for the ITT population.

7.3. Urine Drug Screen, Alcohol and Cotinine Check

Urine drug screen (tetrahydrocannabinol, opiates, cocaine, methamphetamine, barbiturates, and benzodiazepines) and history check by the investigator will be performed for alcohol, and cotinine check at Screening and Day -1.

The urine drug screen results will be presented in a data listing for the ITT population. History check results will be presented in a separate listing. Subjects may undergo an alcohol breath test at the discretion of the investigator, and it will be presented in a separate listing.

7.4. Serology

Serology tests (anti-HIV [HIV-1 and HIV-2] antibodies, hepatitis B surface antigen, hepatitis B surface antibody, hepatitis B core antibody [total or IgG], HBV DNA, hepatitis C antibody, nontreponemal test [e.g., Rapid Plasma Reagins]) will be performed at Screening. The results will be presented in a data listing for the ITT population. A summary table will be presented for serology test results by treatment arm and overall for the ITT and Safety populations.

8. Treatments and Medications

8.1. Prior and Concomitant Medications

Information about prior medications taken by the subject within the 30 days before the administration of study drug (Day 1) will be recorded in the subject's eCRF.

Concomitant medication use will be recorded for medications taken by the subject from the time the subject signs the ICF until the EOS visit. Concomitant medication use is permitted if indicated by the investigator for treatment of an AE.

Prohibited medications during the study include the following:

- Monoclonal antibody or fusion protein or other a biologic agent (including but not limited to tumor necrosis factor- α blockers)
- Any other investigational drug except for the study drug during this study
- Live or live-attenuated vaccine during the study and until 6 months after the study drug administration (Day 1)
- Over-the-counter medications, prescription medications (excluding hormonal birth control), dietary supplements, or herbal remedies excluding the premedications or treatment of AEs.

Prior and concomitant medications will be coded using the World Health Organization Drug Dictionary (WHODD), Version March 2019 or later. It is the investigator's responsibility to ensure that details regarding the medication are adequately recorded in the eCRF.

Medications will be classified as either prior or concomitant. For the purpose of inclusion in prior or concomitant medication tables, incomplete medication start and stop dates on eCRF will be imputed as follows:

- If the stop date is incomplete, the following rules will be applied:
 - Missing day: Assume the last day of the month;
 - Missing day and month: Assume December 31st;
 - Missing day, month, and year: Assume that the medication is continuing;

- In the case of the death of a subject, and if the imputed end date is after the date of death, the end date will be imputed as the date of death.
- If the start date is incomplete, the following rules will be applied. If the stop date is incomplete, imputed end date will be used instead of reported end date:
 - Missing day: Assume the first day of the month;
However, if the partial date and the date of study drug administration (defined as the earliest date recorded on the “Exposure - Injection” page of eCRF) lie within the same month and year and the date of study drug administration is not after the stop date of the medication, set to the date of study drug administration. Otherwise, set to stop date of the medication.
 - Missing day and month: Assume January 1st.
However, if the partial date and the date of study drug administration lie within the same year and the date of study drug administration is not after the stop date of the medication, set to the date of study drug administration. Otherwise, set to stop date of the medication.
 - Missing day, month, and year: Assume date of study drug administration if it's not after the stop date for the medication. Otherwise, set to stop date for the medication.

For the missing day imputation, the following examples should be used for reference:

- Example 1:
Medication start: UNJUN2019
Medication end: 20OCT2019
Date of administration: 16OCT2019
Medication start imputed: 01JUN2019
- Example 2:
Medication start: UNOCT2019
Medication end: 20OCT2019
Date of administration: 16OCT2019
Medication start imputed: 16OCT2019
- Example 3:
Medication start: UNOCT2019
Medication end: 20OCT2019
Date of administration: 24OCT2019
Medication start imputed: 20OCT2019

Relative start day or end day with respect to the dose date of study drug will not be calculated if the medication start date or end date is incomplete.

A prior medication is defined as any medication where the start and stop dates or imputed start and stop dates are before the date of study drug administration or checked as ‘Yes’ for the questionnaire ‘If end date is unknown, was this drug stopped before the administration of study drug?’ in eCRF. A concomitant medication is defined as any medication that has an actual or imputed stop date on or after the date of study drug administration, marked as ongoing or missing or checked as ‘No’ for the questionnaire ‘If end date is unknown, was this drug stopped before the administration of study drug?’ in eCRF.

The total number of prior or concomitant medications and the number and percentages of subjects with at least one prior or concomitant medication will be summarized for the safety population. Prior and concomitant medication data will be presented separately by drug class (using Anatomical Therapeutic Chemical [ATC] Level 2), PT, and treatment arm. At each level of summarization, a subject is counted only once if the subject reported one or more medications at that level. When ATC Level 2 for drug class is not available, Level 1 will be used instead.

All prior and concomitant medications will be presented in data listings for the safety population.

8.2. Study Treatments

The number and percentage of subjects who administered study drug will be presented. The planned dose amount of study drug administration data for CT-P17, US-licensed Humira, and EU-approved Humira will be presented in a summary table using descriptive statistics (n, mean, SD, minimum, median, and maximum) by treatment arm for the safety population. In addition, the number and percentage of subjects who did and did not have whole volume of study drug administered successfully will be presented.

Study drug administration data for CT-P17, US-licensed Humira and EU-approved Humira will be presented in a data listing for the safety population.

9. Pharmacokinetic Analysis

All PK analyses will be performed on the PK population unless otherwise specified.

9.1. Serum Concentrations

Blood samples will be collected from each subject during this study for the determination of the PK of adalimumab administered as CT-P17 or US-licensed Humira or EU-approved Humira. Blood samples for PK analysis of adalimumab will be drawn according to the following schedule and acceptable tolerance window:

- Pre-dose (Day 1, within 60 minutes prior to administration of the study drug)
- 6 hours after the start of administration of the study drug (Day 1, ± 15 minutes)
- 12 hours after the start of administration of the study drug (Day 1, ± 1 hour)
- 24 hours after the start of administration of the study drug (Day 2, ± 2 hours)
- 48, 72, 96, 108, 120, 132, 144, 168, and 192 hours after the start of administration of the study drug (Days 3, 4, 5, 5.5, 6, 6.5, 7, 8, and 9, respectively, ± 2 hours)
- 336 and 504 hours after the start of administration of the study drug (Days 15 and 22, respectively, ± 4 hours)
- 672, 1008, 1344, and 1680 hours after the start of administration of the study drug (Days 29, 43, 57, and 71 (i.e. EOS), respectively, ± 1 day)

Even if an assessment takes place using the given tolerance window, the consecutive assessment will be performed from the baseline time point (prior to start of study drug administration for assessments to be performed before the injection, and after study drug administration for assessments to be performed after the injection).

Serum samples will be analyzed to determine the concentrations of adalimumab using a validated immunoassay.

Serum adalimumab concentrations, collection times, and collection time deviations will be listed for the safety population by actual treatment arm. Serum adalimumab concentrations will be summarized for the PK population by treatment and time point, using descriptive statistics (n, arithmetic mean, SD, %CV, geometric mean, minimum, median, and maximum).

Serum adalimumab concentrations will also be summarized for the PK population by treatment, time point, and ADA status. Based on the immunogenicity data ([Section 10.10](#)) subjects will be assigned either a positive or negative ADA status, if they meet the following criteria:

- Positive ADA status: At least one “Positive” post-treatment result (including unscheduled visit and EOS visit). Subjects will still be assigned a “Positive” ADA status where missing ADA post-treatment results exist alongside a positive result.
- Negative ADA status: All “Negative” post-treatment result (including unscheduled visit and EOS visit). Subjects will still be assigned a “Negative” ADA status where missing ADA post-treatment results exist alongside a negative result.

Individual serum concentration versus time profiles for adalimumab will be presented graphically on both linear and semi-logarithmic scales by treatment and subject using actual sampling times. An overlay plot (Spaghetti plot) of subjects within each treatment will be presented graphically on both linear and semi-logarithmic scales for each treatment using actual sampling times. The mean (\pm SD) serum concentration versus time profiles for adalimumab will be presented graphically on both linear and semi-logarithmic scales by treatment, and also by treatment and ADA status. For ease of presentation, scheduled sampling times will be used to present results for the mean figures.

Below the lower limit of quantification (BLQ) values that occur prior to study drug administration will be treated as zero (0). After study drug administration, all other incidences of BLQs will be treated as missing for serum PK concentrations and PK parameter estimation. Measurable concentrations after consecutive BLQs during the terminal phase will also be set to missing.

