1.4 Clinical Studies

No clinical studies of CT-P17 have been performed. The safety, tolerability, and pharmacokinetics (PK) of Humira (adalimumab) in healthy subjects were evaluated in a series of phase 1 studies.

Study DE024 was a single center, double-blind, randomized, placebo-controlled, parallel-group, ascending single-dose study in healthy male subjects. A total of 80 subjects (60 active and 20 placebo) participated in the study. Active subjects received a single intravenous (IV) dose of 1 mg/kg Humira over 2 to 3 minutes or 0.1, 0.3, and 1 mg/kg Humira via SC injection. Results demonstrated that following SC administration of Humira the mean

maximum observed serum concentration (C_{\max}) and area under the concentration-time curve (AUC) from zero to infinity ($AUC_{0-\infty}$) increased with increasing dose, with dose proportional increases noted at the 0.3 and 1 mg/kg SC doses only. The time to C_{\max} (T_{\max}) ranged from 48 to 336 hours and the mean half-lives ranged from 284 to 433 hours across doses.

Study DE015 was an open-label, randomized, parallel-group, single-dose study to assess the absolute and relative bioavailability of three injectable formulations of human anti-TNF antibody D2E7 in healthy male and female subjects. Subjects received 40 mg D2E7 as three different formulations via IV (50 mg/mL D2E7, with Tween-80) or SC injection (25 mg/mL D2E7, without Tween-80; 50 mg/mL D2E7, with Tween-80; and 50 mg/mL D2E7, without Tween-80). The results indicated that the mean C_{\max} and T_{\max} for the three SC formulations of D2E7 were comparable. The overview and results of Studies DE024 and DE015 can be found in *Clinical Pharmacology and Biopharmaceutics Review(s), FDA*.

Study M10-867 was a phase 1, single-dose, parallel-arm, single-blind, randomized study in healthy adult subjects. A total of 300 subjects were administered two formulations of Humira (40 mg/0.8 mL [50 mg/mL], reference vs. 40 mg/0.4 mL [100 mg/mL], test). The 90% CIs for the ratio of C_{\max} central values (101.9 – 115.2) and the ratio of AUC from time zero to 1344 hours (AUC_{0-1344}) central values (107.2 – 124.9) demonstrated comparable bioavailability of the two formulations. The overview and results of Study M10-867 can be found in the Product Monograph of Humira (*HUMIRA Product Monograph 2018*).

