Continuous variables will be summarized using descriptive statistics: number of subjects (n), mean, standard deviation (SD), minimum, median, and maximum, unless otherwise specified. For the summary statistics of all numerical variables unless otherwise specified, minimum and maximum will be presented to the same number of decimal places as the raw data, mean and median will be presented to one more decimal place than the raw data, and SD will be presented to two more decimal places than the raw data. If the geometric mean is to be presented, it will be set to the same precision as the mean. If the minimum value from the data is zero, then the geometric mean will not be calculated. Point estimates and confidence intervals (CIs) obtained from statistical procedures will be displayed to two decimal places.

For safety laboratory evaluations, for the purpose of summarization, any numeric values recorded below the lower limit or above the upper limit of quantification will be set to the respective limit for all related summaries. In listings, original results containing inequality sign will be displayed, unless otherwise specified.

Unless stated otherwise, all summary tables will present descriptive statistics and/or frequencies by treatment arms or overall (as appropriate), and all data listings will be sorted by treatment arm, subject number, and assessment date or visit date if applicable. In cases where more additional sorting is required, other variables will be included in the sort order as applicable.

Unless otherwise specified, all data collected on the eCRF will be presented in data listings by treatment arm and subject number where applicable.

If there are repeated measurements at a time point, the initial scheduled measurement at that time point will be used in the summary tables. If the initial scheduled measurement at that time point is missing, the next available repeated measurement will be used in the summary tables. The repeated measurements will be listed with indicator. Unscheduled visit results will not be included in the summaries except for determining baseline, but will be presented in data listings.

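### Does treating post-dose BLQ concentrations as missing in the by-time-point tables and mean plots call for a change to the SAP?

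*SAP*

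**What the plan says.** SAP Section 9.1 sets BLQ results before dosing to zero. For BLQ results after dosing the rule is that "all other incidences of BLQs will be treated as missing for serum PK concentrations and PK parameter estimation". The next sentence goes further: "Measurable concentrations after consecutive BLQs during the terminal phase will also be set to missing".

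The section has two descriptive outputs that use these data. For the tables, "Serum adalimumab concentrations will be summarized for the PK population by treatment and time point, using descriptive statistics" (n, mean, SD, %CV, geometric mean, minimum, median, maximum), and they are repeated by ADA status. For the figures, the mean (SD) profiles "will be presented graphically on both linear and semi-logarithmic scales by treatment, and also by treatment and ADA status". No other BLQ rule is given for either, so the missing-value rule governs both.

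SAP Section 5 has two related rules. For safety laboratory data, "any numeric values recorded below the lower limit or above the upper limit of quantification will be set to the respective limit". For any summary, "If the minimum value from the data is zero, then the geometric mean will not be calculated".

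The similarity decision (SAP Section 9.3) uses only AUC0-inf, AUC0-last and Cmax.

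**The concern.** A BLQ result is not a missing observation. The sample was taken and assayed, and the concentration is known to be low. Removing only such values leaves a late mean and median computed among the slower eliminators, so the tail of the mean profile flattens and sits too high. The bias grows with the BLQ share, so it differs between groups that clear the drug at different speeds. The outputs split by ADA status would be the most exposed if antibodies speed clearance, which the documents do not state. The table's n falls but does not separate a BLQ result from a sample never taken. The SAP also looks inconsistent, since safety laboratory values beyond a quantification limit are kept at that limit.

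At stake is how a reader sees the last visits, mainly Days 57 and 71, and possibly whether a difference between arms or ADA strata in the tail is hidden.

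**Working it through.** **Inputs from the documents.** The last samples are at 672, 1008, 1344 and 1680 h (SAP Section 9.1). On half-life, Protocol Section 1.4 reports that "the mean half-lives ranged from 284 to 433 hours across doses", and Section 1.5 uses about 2 weeks (336 h). There are 91 evaluable subjects per arm (SAP Section 5.1). The plan states no LLOQ, BLQ share or late concentration, so it has no figure of its own to reproduce here.

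**Timing.** Day 57 is 1344/433 = 3.1 to 1344/284 = 4.7 half-lives after dosing. Day 71 is 1680/433 = 3.9 to 1680/284 = 5.9. Some BLQ results at these visits are plausible.

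**Direction, without a PK model.** Let p be the BLQ share.

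- Mean of quantifiable values = (mean with BLQ as 0)/(1 − p). For p = 5%, 10%, 20% and 30%, this is 5%, 11%, 25% and 43% higher.
- The printed median is the (1 + p)/2 quantile of all sampled subjects. At p = 20% it is the 60th percentile.

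**Size, under assumptions.** In both models the LLOQ is assumed to be 0.5% to 5% of typical Cmax, half-lives are 284, 336 and 433 h, and there is no ADA effect.

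*Model A:* one-compartment SC, ka 0.012/h (CV 40%), CV of CL/V 35%/30% or 48%/25%, 200,000 profiles per scenario.

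| Day | BLQ share | Planned mean ÷ true mean |
|---|---|---|
| 29 | – | 1.00–1.03 |
| 43 | – | 1.00–1.19 |
| 57 | 0.6–40% | 1.01–1.55 |
| 71 | 2.6–62% | 1.03–2.13 |

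The Day 71 median is 1.03 to 3.5 times true.

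*Model B:* mono-exponential decline from a peak at 132 h, elimination-rate CV 40%, log-SD of peak 0.30, 400,000 profiles per scenario. At 336 h and an LLOQ of 1% to 2% of Cmax, the Day 57 mean is 6% to 13% high and the Day 71 mean 20% to 38% high. Over the full grid, Day 71 runs from +2.6% to +156%.

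**Scale against the profile.** In Model B at 336 h, a typical subject on Day 71 is at 2^(−(1680 − 132)/336) = 2^(−4.61), about 4.1% of peak. With an LLOQ of 1% of Cmax the median reads 31% too high: 4.1% × 1.31 = 5.4% of peak. The shift is about 1.3% of peak, which is slight on the linear plot.

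**Effect on the decision.** Cmax lies far from the tail, and AUC0-last ends at the last quantifiable sample by definition. Recomputing AUC0-last with BLQ as zero up to that sample, instead of missing, changes the geometric mean by a factor of at most 1.00003.

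**What the alternatives would do (Model B, Day 71).**

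- 336 h, LLOQ 1%: the planned mean is 1.198 of true, 1.214 of the zero-substituted mean and 1.197 of the LLOQ/2-substituted mean. Zero therefore gives 1.198/1.214 = 0.987 of true, and LLOQ/2 gives 1.198/1.197 = 1.001.
- 284 h, LLOQ 5% (72% BLQ): planned 2.564 of true; zero 2.564/3.613 = 0.71; LLOQ/2 2.564/2.235 = 1.15.
- Zero also triggers the Section 5 rule that suppresses the geometric mean. At the mildest Day 71 share in Model A (2.6%), the chance of at least one BLQ among 91 subjects is 1 − 0.974^91 = 91% per arm.
- Above 50% BLQ, zero gives a median of 0.

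**The case for a change.** The best case for a change is that the direction of the bias is beyond dispute, two different models show it can be large by Day 71, and the repair is cheap: a sentence, a flag and a row with the number BLQ. Both substitutions land closer to the true mean than the planned rule in the scenarios above. The median would be exact under either one while fewer than half are BLQ. The falling n does not say why values are absent, and readers look at mean plots before listings.

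Most of this stands as description, but it does not carry the change. The large figures come from a tenfold assumed LLOQ range and assumed variability; the same grid also contains a Day 71 bias below 3%, and the upper end moves from 2.13 to 2.56 between models. The differential effect by ADA status needs a clearance effect that the documents do not supply. Between arms randomised 1:1:1 and stratified by weight, gender and center, the distortion largely cancels if BLQ shares are similar. The contrast with safety laboratory data is weak, since that rule is confined to those data and sets values to the limit, which is neither zero nor half the LLOQ.

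Nor is the reader left blind. SAP Section 9.1 lists every concentration with its collection time and plots every subject on both scales. Protocol Section 6.3.1.1 requires an explanation in the eCRF for missed samples. Only a summary count of BLQ results is absent, and analysts can add that row or a footnote without an SAP change.

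**Conclusion.** The observation is correct, but it does not call for a change. The late means and medians describe quantifiable values only and read high. The Day 71 mean ranges from about 3% high to more than double, depending on an LLOQ and variability that the documents do not give. The rule is explicit, prespecified and applied alike to all arms. Cmax, AUC0-last and the 80% to 125% decision do not depend on how the concentration tables treat BLQ, and treating BLQ as missing for parameter estimation should stay in any case.

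The alternatives trade one defect for another: zero usually removes the geometric mean and understates the mean, while LLOQ/2 is nearly exact with few BLQ values but 15% high in the heaviest case. This is a choice of presentation. A reader of the report should take the late part of the mean profiles as conditional on being quantifiable and use the listings and individual plots alongside it.
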